Exercise capacity and cardiac function can be improved in patients with chronic HF by increasing circulation ketone bodies. This can be achieved through a dietary supplement of 3-OHB.

3 Objectives

- 1: To determine uptake kinetics of oral 3-OHB supplements in patients with chronic HF.
2. Furthermore to investigate acute pharmacodynamic effects (i.e. hemodynamic effects) of oral 3-OHB intake by two different ketone-supplements.
- 3: To investigate the effect of 4 weeks modulation of circulating ketone body levels on cardiac function and exercise capacity in chronic HF patients.

4 Design and endpoints

The study consists of one pilot study (KETO-KINETICS) and one main study (KETO-CHF) with a hemodynamic substudy and a metabolic substudy. . The purpose of the pilot study is 1) to establish uptake kinetics and 2) acute hemodynamics of two oral ketone dietary supplements, and 3) differentiate acute and chronic effects of oral ketone supplementation. There will be separate participant informations and consent forms for the substudies. Thus participants can opt only to participate in one substudy if they prefer. The study days are outlined in table 1-3.

Original protocol title: *Modulation of circulating levels of the ketone body 3-hydroxybutyrate in patients with chronic heart failure: Cardiovascular and metabolic effects*

[name], Læge, PhD-studerende, Afd. for Hjertesygdomme, Aarhus Universitetshospital Skejby, Aarhus, Denmark

Scientific Committee ref.: 1-10-72-362-18

KETO-KINETICS: KETO-CHF pilot study:

Design: 10 patients are studied after an overnight fast, in random order on 3 visits, during a) oral intake of 36 g Perfect Keto Oral 3-OHB supplement, b) oral intake of 25 g HVMN Ketone Ester, and c) during a placebo isocaloric drink (similar energy content as the 36 g 3-OHB dose, containing 1:1:2 mixtures of dextrose, fructose, and maltodextrin) [6].

Endpoints: Cardiac output, venous 3-OHB levels, LVEF, LV global strain.

Methods: Swan-Ganz Monitoring, Echocardiography, ECG and blood pressure will be recorded hourly. 3-OHB levels are measured by venous blood samples every 60 minutes. Sampling will be performed hourly from 1 hour before till 5 hours after oral intake.

KETO-CHF: Randomized, double blind crossover study with 20 stable chronic HF patients.

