Design: Patients are studied after 4 weeks of oral 3-OHB three times daily (36 g "Perfect Keto Base" or 25g HVMN Ketone Ester depending on the outcome of KETO-KINETICS three times) and 4 weeks isocaloric placebo-drink. Both "Perfect Keto Base" (Perfect Keto, Glendale Heights, IL, USA) and HVMN Ketone Ester (HVMN, San Francisco, CA, USA) are a commercially available ketone diet supplements.

Endpoints: 1) Cardiac output (primary), mixed venous saturation (SVO2), pulmonary wedge pressure 2) Rest/Peak Exercise Echocardiography (LVEF, Global Strain), 3) Cardiopulmonary exercise test, 4) Whole-body substrate metabolism, insulin signalling and lipolysis.

Methods: Swan-Ganz monitoring, echocardiography, exercise capacity, whole-body glucose, FFA and protein metabolism will be examined using isotope tracer techniques. Furthermore, muscle biopsies will be drawn for studies of insulin signalling and lipolysis (chapter 5).

[figure not shown]

Figure 1: Patient Inclusion flowchart

Table 1: Study Visits Overview

Visit	V0 Screening	Teleph. Contact	V1 Randomizat ion	V2 Hemodynamic examination 1	V3 Metabolic Examinations 1	V4 Hemodynamic examinations 2	V5 Metabolic Examinations 2
Time (Days, Weeks, Months)	-4W to 0	-3½ W-0W	0	3-5W	3-5W	10-12W	10-12W
General							

Original protocol title: *Modulation of circulating levels of the ketone body 3-hydroxybutyrate in patients with chronic heart failure: Cardiovascular and metabolic effects*

[name], Læge, PhD-studerende, Afd. for Hjertesygdomme, Aarhus Universitetshospital Skejby, Aarhus, Denmark
Scientific Committee ref.: 1-10-72-362-18

Informed consent	X						
In-and exclusion criteria	X		X				
Relevant medical/surgical history			X				
Relevant concomitant medication (1)			X				
Randomize patient			X				
Study medication							
Delivery	(Trial period)		X				
Crossover					X		
Clinical assessment							
NYHA class			X	X	X	X	X
Height			X				
Weight			X	X	X	X	X
Echocardiography				X		X	
Swan-Ganz Monit.				X		X	
CPX-test				X		X	
Whole-Body Metabolism					X		X
Blood Samples				X	X	X	X
Muscle Biopsies					X		X
ECG			X	X		X	
Blood pressure, heart rate	X		X	X	X	X	X
Safety							
Reporting of: -Endpoints -SUSARs -selected AEs		X	X	X	X	X	X

Table 2: Hemodynamic study day overview

Time	07.30	08.30	09.15	09.30	10.30	10.50	11.10	11.30	12.30
Arrival			X						
Swan Ganz				X					
Exercisetest						X			
Blood Samples				X		X	X	X	X
Echocardiography				X		X	X	X	X
Invasive measurements				X		X	X	X	X

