5.1.4 Muscle biopsies

Samples are taken from the vastus lateralis by sterile technique. Proteins involved in insulin-signalling and lipolysis will be determined by Western Blot technique.

5.1.5 Cardiopulmonary Exercise Test:

Cardiopulmonary exercise capacity will be performed using a staged bicycle exercise test with measurements of oxygen consumption and carbon dioxide excretion. After resting measurements are obtained patients will start exercising at 0 watts and using 3 minute intervals increase to 20 watts and then with 10 watt increments every 3 minutes until peak exercise (Borg > 18). At each level of exercise hemodynamic and echocardiographic measurements will be recorded. A preliminary exercise test will be performed prior to the baseline study to make the patient familiar with the procedure.

5.1.6 Blood samples:

Venous blood samples for measurements of plasma insulin, free fatty acids, glucose, ketone bodies, lactate, haemoglobin, P-Na⁺, P-K⁺. Will be measured three times during each visit P-LDL, P-HDL and P-Cholesterol (total), prostaglandin E2, I2, F2 α , thromboxane A, erythropoietin, thrombopoietin and granulocyte stimulating factor will be measured twice during the pilot study and the hemodynamic study days.

6 Power calculation and statistics

Power calculations

In the pilot study we plan to include 8 patients. However, if necessary because of drop-outs or missing values up to 10 patients will be included.

Coefficiency of variation (CV) regarding Cardiac output by pulmonary artery catherization is determined to be 4 % [19]. By enrolling 8 patients in the KETO-KINETIC pilot study, we will be able to detect a relative difference of 6% with a power of 90% and a two-sided significance level of 5%. In the KETO-CHF study by enrolling 20 patients in the hemodynamic examinations, and allowing up to 20 % missing values, we will be able to determine a relative difference of 4 %, and thus detect changes related to clinical outcome [20], with a power of 90% and a two-sided significance level of 5%.

In the metabolic studies, previous studies have shown an SD of the difference of 8% and an effect size of 10%. With power and significance level as described above a sample size of 8 patients are needed. To allow 20% missing values 10 patients will be included in the metabolic studies.

Reporting of endpoints:

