For these studies normally distributed variables will be presented as mean \pm SD. Non-parametric statistics and appropriate log-transformation will be performed if assumption of normality is not met. A two-tailed p value of 0.05 or less will be considered statistically significant.

Differences will be compared by appropriate paired statistical tests. Regression analysis will be performed and correlation coefficients will be presented when appropriate.

7 Patient recruitment

Patients with stable HF will be recruited from the outpatient HF clinic at Aarhus University Hospital.

Inclusion criteria: Chronic HF: NYHA class II-III, left ventricular ejection fraction (LVEF) <40%

Exclusion Criteria: Diabetes or HbA1c >48 mmol/mol, significant cardiac valve disease, severe stable angina pectoris, severe comorbidity as judged by the investigator, inability to give informed consent

Original protocol title: *Modulation of circulating levels of the ketone body 3-hydroxybutyrate in patients with chronic heart failure: Cardiovascular and metabolic effects*

[name], Læge, PhD-studerende, Afd. for Hjertesygdomme, Aarhus Universitetshospital Skejby, Aarhus, Denmark
Scientific Committee ref.: 1-10-72-362-18

Recruitment and informed consent

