Adverse Effects of study medication

Ketone supplements may cause mild gastrointestinal discomfort and mild headaches in the first days entering a regimen. Patients are therefore subjected to a four day run-in period (2 days of KETO-base supplement and 2 days of placebo) before randomization. Only those able to tolerate side-effects will be included in the study. In case of unacceptable side-effects during the study period, doses will be reduced step-wise until reaching no – or accepted level of side-effects. Blood samples for determination of K^+ , Na^+ , Ca^{2+} and Mg^{2+} will be drawn after two- four days of treatment and 1-2 weeks later during the study period in the first 6 patients in the KETO-CHF study. If deemed necessary by the investigators this procedure will be carried out in the remaining 14 patients as well.

Potential benefits for the participants

Participants will potentially benefit from the 3-OHB supplement applied in this study. Participants with HFrEF will be evaluated for their present cardiac status. The right sided heart catherization is the gold standard to obtain measures of cardiac output and importantly cardiac filling pressures (preload) conditions. During daily practice, HFrEF patients often have their heart failure medication adjusted after right sided heart catherization as non-invasive assessment of preload conditions are often very difficult or impossible to obtain. Thus, each HFrEF participant will benefit by having their heart failure and diuretic treatment re-evaluated and eventually adjusted or intensified. Furthermore, the study could contribute with pivotal information on a potential future treatment of patients suffering from HFrEF, and determine whether a clinical trial of long-term hyperketonaemia should be initiated.

10 Ethical considerations

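### KETO-CHF is a two-period crossover, but section 6 does not commit to a period-adjusted analysis, and the plan does not keep heart failure treatment stable, or schedule its recording, between the two catheterisations

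*Combined protocol and SAP*

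**What the plan says.** Section 4 describes KETO-CHF as a "Randomized, double blind crossover study with 20 stable chronic HF patients", with four weeks of 3-OHB and four weeks of isocaloric placebo. The primary endpoint is cardiac output. In Table 1, Swan-Ganz monitoring falls at V2 (weeks 3-5) and V4 (weeks 10-12), so there is one catheterisation per period.

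For the comparison, section 6 says only "Differences will be compared by appropriate paired statistical tests". It adds log-transformation or non-parametric methods if normality fails, and regression where suitable. It names no period or sequence term. The available text does not say how sequences are allocated.

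Section 9, under potential benefits, notes that "HFrEF patients often have their heart failure medication adjusted after right sided heart catherization" and concludes that "each HFrEF participant will benefit by having their heart failure and diuretic treatment re-evaluated and eventually adjusted or intensified". It gives no timing. Table 1 marks concomitant medication at V1 only; the footnote to that row is not in the available text. Section 7 lets investigators receive medical-record information, including medicine intake, and section 8 provides for source records and a CRF. Neither schedules the capture of treatment changes.

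**The concern.** In a two-period crossover, anything that shifts the outcome between periods enters the active-minus-placebo difference with opposite sign in the two sequences. A plain paired test treats that shift as noise when the sequences are equal in size, and as partly treatment effect when they are not.

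The plan itself supplies a possible source. The first catheterisation ends period 1, and the protocol presents treatment adjustment after catheterisation as a benefit of taking part. Changes in heart failure drugs or diuretics between V2 and V4 could move cardiac output and wedge pressure. Because the wording leaves the method open, the choice between a paired and a period-adjusted test could also be made after the data are seen. At stake are power near the 4% target and a small conditional bias if completers are unequal.

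**Working it through.** **Inputs from the documents.** 20 patients, up to 20% missing (so 16 completers), a 4% target difference, a 4% CV for cardiac output, and two-sided 5% (section 6).

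**Assumptions.** The common period shift π is 0 to 4% of cardiac output; the documents give no figure. The SD of the within-patient difference is 5.66% (4% × √2, CV read as single-measurement) or 4% (CV read as that SD).

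**The plan's own figure.** Section 6 claims 90% power for 4%. A paired t-test with 16 pairs gives 75.3% at SD 5.66% and 96.2% at SD 4%, so 90% is not reproduced under either reading. The present point does not depend on this.

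**Model.** Let D = active − placebo, with n1 completers on active first, n2 on placebo first and n = n1 + n2. The mean of D is τ − π in the first sequence and τ + π in the second.

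- Paired estimate: the mean of all D. Its bias is π × (n1 − n2)/n in size. Its estimated variance is inflated to SD² + 4π²·n1·n2/[n(n − 1)].
- Period-adjusted estimate: the average of the two sequence means of D. Its bias is 0, its SE is ½·SD·√(1/n1 + 1/n2), and it has n − 2 degrees of freedom.

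At 8:8, SD 5.66% and π = 4%, the paired test uses √(32 + 4×16×64/240) = √49.1 = 7.0% in place of 5.66%. At π = 2% it uses √(32 + 4.27) = 6.0%.

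**Power at 8:8, τ = 4%, uniform shift (simulation; paired v adjusted).**

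| π | SD 5.66% | SD 4% |
|---|---|---|
| 0 | 75 v 75 | 96 v 96 |
| 2% | 71 v 75 | 93 v 96 |
| 4% | 58 v 75 | 81 v 96 |

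At π = 1% and SD 5.66% the figures are 74 v 75, a gain of under 1 point.

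**Shifts in some patients only (8:8, SD 5.66%).**
- Half shifted by 4% in the same direction: 66 v 70.
- A quarter shifted by 8% in the same direction: 58 v 61. If these changes were deferred, power would return to 75.
- A quarter shifted by 8% in random directions: about 58 either way.

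**Bias of the paired estimate.** At 9:7 it is π × 2/16: 0.25 points for π = 2% and 0.5 for 4%. At 10:6 it is π × 4/16: 0.5 and 1.0. Either sign is possible. The SE is 5.66/√16 = 1.4 or 4/√16 = 1.0. At 9:7, π = 2% and SD 5.66%, paired power is 65% or 76% depending on which sequence is larger, against 74% adjusted. The 76% comes from the bias.

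**Type I error of the paired test.** At 8:8, SD 5.66% and π = 4% it is about 2%. Up to 10:6 it stays at or below 5%, within simulation error. At 11:5 it is about 6.5% (π = 2%) and 9% (π = 4%) at SD 5.66%, and about 7.5% and 10% at SD 4%.

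**How likely is imbalance?** With 10:10 allocation and four losses at random, the hypergeometric probabilities are 42% for 8:8, 50% for 9:7 and 9% for 10:6. An 11:5 split cannot then occur. Under simple randomisation (an assumption) 16 completers split 11:5 or worse with probability 21%.

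**The case against.** The strongest reply is that the mechanism is inferred. The section 9 passage describes benefits, does not name V2 and does not separate the pilot from KETO-CHF, and "eventually" may mean only "possibly". Patients are recruited as stable. The word "appropriate" leaves room for a period-adjusted method, and section 6 also mentions regression. All of this stands: the plan permits a good analysis and does not show that a period effect will occur. It also fixes neither the analysis nor the timing of changes.

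Second, individual changes need not share a direction, and if they go both ways a period term recovers nothing. This also stands, and it makes trial conduct at least as important as the model. Nor does a period term remove changes prompted by filling pressures measured under the period 1 product; these act like carry-over.

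Third, the true effect may be well above 4%: section 1 cites a 40% rise in cardiac output, although during infusion. At a true effect of 8%, both analyses exceed 99% power for mean shifts up to 2%.

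A reader might infer that treatment changes go unrecorded. The documents do not support that. Record access and source data are provided for, and the missing footnote may say more. What is absent from the available text is scheduled capture.

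**Conclusion.** The point holds as a moderate weakness that is cheap to remedy. The primary analysis of a two-period crossover should commit to a period term, and background treatment should be protected and tracked between the two catheterisations. If there is a common shift of 2 to 4%, the paired test loses about 4 to 17 points of power at 8:8 with SD 5.66%, and about 3 to 15 points with SD 4%, for a true effect of 4%. With unequal completers it is also biased by 0.25 to 1.0 points at 9:7 to 10:6. That bias is conditional on the split and averages to zero over random sequences and losses. For mean shifts of 1% or less the gain at 8:8 is under 1 point.

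It would be too strong to call the paired test invalid. With equal sequences it is unbiased and conservative, and its type I error exceeds 5% only at splits such as 11:5, which require unbalanced allocation when 16 of 20 complete. It would also be too strong to say that treatment will change between V2 and V4 in every patient. The size, direction, frequency and timing of such changes are all assumptions here.

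**What to change.** 1. In section 6, prespecify for the KETO-CHF primary endpoint a mixed model with treatment and period as fixed effects and patient as random, or the equivalent two-sequence t-test on within-patient period differences. If normality fails, use a rank-sum test of those differences between sequences.
2. Allocate the two sequences in balanced blocks.
3. Where clinically safe, defer non-urgent heart failure and diuretic changes until after V4, leaving urgent changes unrestricted. Record concomitant medication at V2 to V5.
4. Keep all patients in the primary analysis whether or not their treatment changed. An analysis without those changed between V2 and V4 is exploratory only: it conditions on a post-randomisation event that the period 1 product may have prompted.

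**Cost.** One degree of freedom. With no period effect, power falls from 75.3% to 74.9% at 8:8 (SD 5.66%) or from 96.2% to 96.0% (SD 4%), and by about 1 to 3 points at 10:6. Section 6 and the benefit wording in section 9 need amending, possibly the participant information too, and one row of Table 1 needs extra marks. Non-urgent changes would wait roughly 5 to 9 weeks (10 − 5 to 12 − 3).

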Original protocol title: *Modulation of circulating levels of the ketone body 3-hydroxybutyrate in patients with chronic heart failure: Cardiovascular and metabolic effects*

[name], Læge, PhD-studerende, Afd. for Hjertesygdomme, Aarhus Universitetshospital Skejby, Aarhus, Denmark
Scientific Committee ref.: 1-10-72-362-18

3-OHB/placebo ingestion	x
End of study day	x

Table 3: Metabolic study day overview

Time	07.30	08.30	09.30	10.30	11.30	12.30	13.30	14.30
Arrival		x						
Basal period								
3-OHB sipping								
3-OHB sipping + Clamp								
[3- ³ H]Glucose-Infusion								
[9,10- ³ H]Palmitate-infusion								
Muscle Biopsy			x					x
Blood samples	x		x	x	x	x	x	

5 Methods

5.1.1 Swan-Ganz Monitoring:

This is a standard procedure at the clinical research site and will be performed in a dedicated cardiac catheter lab with experienced physicians. Standard triple-lumen Swan-Ganz thermister and balloon-tipped catheters will be used. Catheters will be introduced using the internal jugular vein, using ultrasound guidance, and advanced using pressure waveform and fluoroscopy into the pulmonary artery. Cardiac output will be measured using the thermodilution method.

Measurements will be made at rest, during peak exercise and post-exercise.

5.1.2 Rest/Peak Exercise Echocardiography:

We intend to use a GE VIVID 7 or 9E system (GE Medical System, Horten, Norway) with a 2.5-MHz transducer for transthoracic echocardiography. For image analysis EchoPAC (GE-Vingmed Ultrasound, Horten, Norway) will be used. All measurements will be the averaged over 3 consecutive heart cycles in end-expiration. 2D echocardiography will be performed according to national guidelines [14]. In case of poor image quality, a contrast agent (SonoVue/Optison) will be used to opacify the left ventricle (LV) [15, 16]. Regarding LV measurements, the following parameters will be recorded: 2D [16], regional wall motion score (16 segment model), LVEDV and LVESV, left atrial volume, tissue Doppler study of the mitral annulus and LV strain and strain-rate[17].

5.1.3 Whole-body metabolism:

Glucose metabolism is determined by isotope dilution technique with constant infusion of [3-³H] glucose (12 µCi / min) from two hours before and 60 minutes after intake of ketones or isocaloric placebo.

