FFA Turnover is determined by isotope dilution technique with 2 times 1-hour constant infusion of [9,10-³H] palmitate (0.3 µCi / min, totalling 36 µCi) before and 60 minutes after oral intake. Blood samples to determine FFA concentration and specific activity will be taken at baseline and after 30, 40, 50 and 60 minute infusion. Plasma FFA (palmitate) concentration and specific activity are determined by HPLC[18].

Original protocol title: *Modulation of circulating levels of the ketone body 3-hydroxybutyrate in patients with chronic heart failure: Cardiovascular and metabolic effects*

[name], Læge, PhD-studerende, Afd. for Hjertesygdomme, Aarhus Universitetshospital Skejby, Aarhus, Denmark

Scientific Committee ref.: 1-10-72-362-18

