The risk for adverse health effects from cancer is proportional to the amount of radiation dose absorbed and strongly dependent on age. When reviewing the numbers below, the natural incidence of fatal cancer in Denmark of about 25% and the 5-year mortality of 43% in Danish heart failure patients [2] should be taken into account. Radiation doses for the KETO-KINETICS and Keto-CHF study is 6 mSv and 4 mSv each respectively, corresponding to IRCP category IIb. Thus, participation in one study increases cancer risk from 25% to 25.02% in the KETO-CHF study and 25.03% in the KETO-KINETICS study.

Right heart catheterization

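### Must the single KETO-CHF radiation figure (4 mSv, 25.02% cancer risk) be restated because it may leave out the tritium tracers?

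*Combined protocol and SAP*

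**What the plan says.** Section 9 (Radiation) gives one dose per study: "Radiation doses for the KETO-KINETICS and Keto-CHF study is 6 mSv and 4 mSv each respectively". It puts the resulting cancer risk at 25.02% for KETO-CHF and 25.03% for KETO-KINETICS, against a baseline of about 25%. It does not say which procedures these figures cover.

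The exposures are described elsewhere:

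- **Catheterisation.** Section 5.1.1 has the catheter "advanced using pressure waveform and fluoroscopy into the pulmonary artery". The pilot studies patients "in random order on 3 visits" with Swan-Ganz monitoring. Table 1 marks Swan-Ganz monitoring in KETO-CHF at V2 and V4 only.
- **Tracers.** Section 5.1.3 gives tritiated "glucose (12 µCi / min) from two hours before and 60 minutes after intake" without a total, and tritiated palmitate "totalling 36 µCi". Table 1 marks whole-body metabolism at V3 and V5 only.
- **Participation.** Section 4 describes a hemodynamic and a metabolic substudy, each with its own participant information and consent form, and adds: "Thus participants can opt only to participate in one substudy if they prefer".
- **Numbers.** Section 4 plans 20 KETO-CHF patients. Section 6 reaches its detectable difference "by enrolling 20 patients in the hemodynamic examinations", and says "To allow 20% missing values 10 patients will be included in the metabolic studies".

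**The concern.** A patient could be exposed to fluoroscopy only, to tracers only, or to both, and one dose cannot be exact for all three. The 6 to 4 ratio of the two study doses equals the 3 to 2 ratio of catheterisation days, so the KETO-CHF figure looks as if it contains nothing for the tracers. The glucose tracer has by far the larger activity of the two, yet only palmitate has a printed total.

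At stake is disclosure. This paragraph is the protocol's only statement of radiation dose and cancer risk. If the tracers were left out, it would understate the exposure of patients in both substudies.

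**Working it through.** **1. The plan's own risk figures.** Slope = (stated risk − 25%) / stated dose.

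- KETO-CHF: 0.02 / 4 = 0.005 percentage points per mSv.
- KETO-KINETICS: 0.03 / 6 = 0.005 percentage points per mSv.

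Both figures reproduce on one slope, so there is no arithmetic error.

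**2. Dose per catheterisation day.** KETO-KINETICS: 6 / 3 = 2 mSv. KETO-CHF: 4 / 2 = 2 mSv. No tracers are described for the pilot, so catheterisation at the pilot's implied dose would use up the whole 4 mSv. This is an inference from figures printed in whole mSv.

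**3. Tracer activity as written** (1 µCi = 0.037 MBq).

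- Palmitate: 0.3 µCi/min × 120 min = 36 µCi per day, matching the stated total. Over two days this is 72 µCi, or 2.7 MBq.
- Glucose: the duration wording is ambiguous and the bars of Table 3 are not legible in the text reviewed, so 120 to 180 minutes is assumed. 12 × 120 = 1,440 µCi (53.3 MBq) and 12 × 180 = 2,160 µCi (79.9 MBq) per day. Over V3 and V5 this is 106.6 to 159.8 MBq.

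**4. Added dose.** The documents give no tritium dose coefficient, so a range is assumed. Added dose = activity × coefficient; risk = 25% + 0.005 × total dose in mSv.

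| Assumed mSv per MBq | Glucose tracer, two days (mSv) | Both substudies, 4 + tracer (mSv) | Risk, both substudies |
|---|---|---|---|
| 0.001 | 0.11–0.16 | 4.1–4.2 | 25.02% |
| 0.010 | 1.07–1.60 | 5.1–5.6 | 25.03% |
| 0.018 | 1.92–2.88 | 5.9–6.9 | 25.03% |
| 0.042 | 4.48–6.71 | 8.5–10.7 | 25.04–25.05% |

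The table takes 4 mSv as the catheterisation dose. Palmitate adds at most 2.7 × 0.042 = 0.11 mSv.

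**5. Where the printed figures would still hold.** The combined dose rounds to 4 mSv while the tracers add less than 0.5 mSv: 0.5 / 159.8 = 0.0031 and 0.5 / 106.6 = 0.0047 mSv per MBq. The risk still rounds to 25.02% while they add less than 1 mSv, since 25 + 0.005 × 5 = 25.025: 1 / 159.8 = 0.0063 and 1 / 106.6 = 0.0094 mSv per MBq. All four thresholds lie inside the assumed range.

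**6. Which groups are planned.** Section 4 gives 20 patients, and the electrolyte checks in Section 9 (first 6, remaining 14) also make 20. With 20 in the hemodynamic part, the 10 metabolic patients come from the same 20 if both targets are met. The tracers-only group is allowed but has no planned members.

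**The case for a change.** The strongest case for a change needs no outside coefficient. If F is the fluoroscopy dose and T the tracer dose, one exact figure for all three groups requires F = T = F + T, which is possible only when both are zero. The combined group could be 10 of 20 patients. Section 9 gives separate paragraphs to blood sampling, catheterisation, echocardiography and muscle biopsies, but none to the injected tracers. The protocol goes to the ethics committee, and a three-row table would be cheap.

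Part of this stands. The coverage of the 4 mSv is not stated, and a tracers-only patient would receive T, which need not be 4 mSv. The rest is weaker:

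- Exact equality is not the test for figures printed in whole mSv. The combined dose can still round to 4.
- The Radiation paragraph names no source at all, fluoroscopy included, so its silence on tracers is not evidence that they were excluded. The figure may also have been meant for the hemodynamic days alone.
- The larger doses depend on one printed infusion rate, an uncertain duration and a coefficient assumed over a 42-fold range. Quoting only its upper part would hide that the lower part agrees with the protocol.
- Separate substudy participant information is the natural place for substudy doses. It was not available for this review, so nothing can be said about what participants were told.

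**Conclusion.** No change to the plan follows. The protocol does not say which procedures its 4 mSv covers, and it leaves the glucose total to be worked out from a rate and a time window. Nothing in it shows that the 4 mSv or the 25.02% is wrong. The matching 2 mSv per catheterisation day makes omission of the tracers plausible but does not prove it.

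Over the full assumed coefficient range, and with 120 to 180 minutes of glucose tracer per day, the combined dose is 4.1 to 10.7 mSv and the risk 25.02% to 25.05%. The worst case is about 0.03 percentage points above the printed risk. A longer infusion at the written rate would raise the dose in proportion. The radiation category named in the paragraph cannot be checked, because the protocol does not give its limits.

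The figure enters no endpoint, power calculation or analysis. A sentence naming the procedures covered would help a reader, but the study's procedures and conclusions do not depend on it.
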